3.0 STUDY ENROLLMENT AND WITHDRAWAL

3.1. Baseline

The screening phase of the trial is designed to meet two objectives:

1. Patient Consent.
2. Determine study patient eligibility and access site for the procedure.

3.2. Informed Consent

Informed Consent will be obtained from all prospective subjects prior to beginning any study activities. All aspects of the trial including that participation is voluntary, will be explained and the patient will have the opportunity to have their questions answered before deciding whether to participate. Patients who agree to participate and sign the informed consent document will be given a copy of their signed consent to take home with them.

Upon completion of the screening process, the patient's case will be presented to the site heart team. If after presentation to the site heart team it is agreed by the members the patient is a suitable candidate, the patient will be presented to the executive committee of the trial. If after the conference call 2/3 of the executive committee members agree, the patient is enrolled in the trial.

3.3 Eligibility Process

All patients with severe tricuspid regurgitation and symptoms who are high risk or inoperable will be screened for study inclusion. Patients must have all inclusion criteria, and be free from all exclusion criteria. Screening and enrollment logs will be maintained. Reasons for screen failures will be documented. The full description and timing of screening tests can be found in Table 1.

3.4 Participant Inclusion Criteria:

In order to be eligible to participate in this study, an individual must meet all of the following criteria

1. Patients must be at least 21 years old.
2. The patient must have severe, symptomatic (ACC/AHA Stage D symptoms) tricuspid regurgitation (TR) as assessed by 2D echocardiogram with evidence of peripheral and central venous congestion (specifically lower extremity edema and abdominal ascites requiring diuretics.)
3. The patient must be evaluated by a “heart team” of physicians including an interventional cardiologist, cardiothoracic surgeon, heart failure specialist, and imaging specialist, and presented for review at a local multi-disciplinary conference. By consensus, the heart team must agree (and verify in the case review process) that valve implantation will likely benefit the patient.
4. The heart team must agree that medical factors preclude operation, based on a conclusion that the probability of death or serious, irreversible morbidity exceeds the probability of meaningful improvement. Also, other factors which may increase the patients perceived surgical risk for inclusion in the trial will be clearly delineated if they are present. These include, but are not limited to the following as defined by VARC 2: Frailty, Hostile chest, porcelain aorta, IMA or other critical conduit crossing the midline or adherent to the posterior table of sternum, severe right ventricular (RV) dysfunction. The surgeons' consultation notes shall specify the medical or anatomic factors leading to that conclusion. At least one of the cardiac surgeon assessors must have interviewed and examined the patient.
5. The study patient provides informed consent and agrees to comply with all required post-procedure follow-up visits, including annual visits up to 5 years.
6. Mean diameter of the IVC at the right atrial junction or superior most hepatic vein $\leq 30.5\text{mm}$

3.5 Participant Exclusion Criteria:

Patient or Subject will be excluded from the study if any of the following conditions are present:

1. Heart Team assessment of operability (the heart team considers the patient to be a good surgical candidate).
2. Evidence of an acute myocardial infarction ≤ 1 month (30 days) before the intended treatment [defined as: Q wave MI, or non-Q wave MI with total CK elevation of CK-MB \geq twice normal in the presence of MB elevation and/or troponin level elevation (WHO definition)].
3. Untreated, severe, left sided valvular heart disease including mitral regurgitation or stenosis, and aortic regurgitation or stenosis.
4. Mean pulmonary artery pressures $\geq 40\text{mmHG}$ and PVR > 4 woods units as assessed by right heart catheterization.
5. Any therapeutic invasive cardiac procedure resulting in a permanent implant that is performed within 30 days of the index procedure. Examples of permanent implant would include any new heart valve. Implantation of a permanent pacemaker is excluded.
6. Patients with planned concomitant surgical or transcatheter ablation for Atrial Fibrillation.
7. Leukopenia (WBC < 3000 cell/mL), acute anemia (Hgb < 9 g/dL), Thrombocytopenia (Plt $< 50,000$ cell/mL).
8. Hemodynamic or respiratory instability requiring inotropic support, mechanical ventilation or mechanical heart assistance within 30 days of screening evaluation.
9. Need for emergency surgery for any reason.
10. Left ventricular ejection fraction $< 40\%$.
11. Echocardiographic evidence of intracardiac mass, thrombus or vegetation.
12. Active upper GI bleeding within 3 months (90 days) prior to procedure.
13. A known contraindication or hypersensitivity to all anticoagulation regimens, or inability to be anticoagulated for the study procedure.

14. Recent CVA clinically confirmed (by neurologist) or neuroimaging confirmed stroke or transient ischemic attack (TIA) within 6 months (180 days) of the procedure.
15. Estimated life expectancy < 1 year from conditions other than TR.
16. Expectation that patient will not improve despite treatment of tricuspid regurgitation
17. Currently participating in another investigational cardiac device study or any other clinical trial, including drugs or biologics. Note: Trials requiring extended follow-up for products that were investigational, but have since become commercially available, are not considered investigational trials.
18. Active bacterial endocarditis within 6 months (180 days) of procedure.
19. Patients with signs or symptoms of SVC syndrome, or hepatic cirrhosis not felt due to passive congestion from TR.
20. Subject unable to personally provide informed consent
21. FEV1<30% of predicted²⁹
22. Model for End State Liver Disease (MELD) score ≥21 (calculated per reference study ³⁰) for patients not on blood thinners

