2.2.2 Core Lab

Either concomitantly or after decision by the local heart site to presentation to the executive committee, baseline echocardiograms and CT scans will be reviewed by the coordinating center (Henry Ford Hospital) to confirm severe TR and anatomic suitability for implant.

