2.2.3 The Executive Committee

The purpose of presentation of patients to the executive committee is to provide additional consultation from experts to further review and approve the selection prior to the patient being enrolled in the trial. The executive team will be comprised of the site PI from each site. The presentation will occur in the form of a conference call which is open to any member of the individual sites included in the HOVER trial. During the executive committee conference call, the local site will verify that the patient meets the

inclusion, and is free from exclusion criteria for the trial. The local site will present the patient's case for committee review. Any questions the executive committee may have regarding the case will be addressed during this call. If after the case presentation, 2/3 of the executive committee agree the patient is suitable for CAVI, the patient will be enrolled in the trial and an implantation date will be set. Documentation of approval for the trial of the patient by the executive committee will be added to the patient's chart. If all members of the executive committee are unable to convene on one conference call, the case will be presented individually to members of the committee in separate phone calls.

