APPENDIX D: INCLUSION/EXCLUSION CHECKLIST

I. Study Information

Protocol Title:	Heterotopic Implantation Of the Edwards-Sapien 3 Transcatheter Aortic Valve in the Inferior Vena cava for the treatment of severe tricuspid Regurgitation
IRB Number:	
Principal Investigator:	[name]

II. Inclusion/Exclusion Criteria

Inclusion Criteria (From IRB-approved protocol)	Yes	No	Supporting Documentation*
1. Patients must be at least 21 years old			
2. The patient must have severe, symptomatic (ACC/AHA Stage D symptoms) tricuspid regurgitation (TR) as assessed by 2D echocardiogram with evidence of peripheral and central venous congestion (specifically lower extremity edema and abdominal ascites requiring diuretics.)			
3. The patient must be evaluated by a "heart team" of physicians including an interventional cardiologist, cardiothoracic surgeon, heart failure specialist, and imaging specialist, and presented for review at a local multidisciplinary conference. By consensus, the heart team must agree (and verify in the case review process) that valve implantation will likely benefit the patient.			

4. The heart team must agree that medical factors preclude operation, based on a conclusion that the probability of death or serious, irreversible morbidity exceeds the probability of meaningful improvement. Also, other factors which may increase the patients perceived surgical risk for inclusion in the trial will be clearly delineated if they are present. These include, but are not limited to the following as defined by VARC 2: Frailty, Hostile chest, porcelain aorta, IMA or other critical conduit crossing the midline or adherent to the posterior table of sternum, severe right ventricular (RV) dysfunction. The surgeons' consultation notes shall specify the medical or anatomic factors leading to that conclusion. At least one of the cardiac surgeon assessors must have interviewed and examined the patient.
			

5. The study patient provides informed consent and agrees to comply with all required post-procedure follow-up visits, including annual visits up to 5 years
			
Exclusion Criteria (From IRB-approved protocol)			

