14. Recent CVA clinically confirmed (by neurologist) or neuroimaging confirmed stroke or transient ischemic attack (TIA) within 6 months (180 days) of the procedure			
15. Estimated life expectancy < 1 year			

16. Expectation that patient will not improve despite treatment of tricuspid regurgitation			
17. Currently participating in another investigational cardiac device study or any other clinical trial, including drugs or biologics. Note: Trials requiring extended follow-up for products that were investigational, but have since become commercially available, are not considered investigational trials			
18. Active bacterial endocarditis within 6 months (180 days) of procedure			
19. Patients with signs or symptoms of SVC syndrome, or hepatic cirrhosis not felt due to passive congestion from TR			
20. Subject unable to personally provide informed consent			
21. FEV1<30% of predicted			
22. MELD score >21			

*All subject files must include supporting documentation to confirm subject eligibility. The method of confirmation can include, but is not limited to, laboratory test results, radiology test results, and medical record review.

III. Statement of Eligibility

This subject is **eligible** / **ineligible** for participation in the study.

Signature:	Date:
Printed Name:	

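### The signed eligibility checklist in Appendix D does not reproduce sections 3.4/3.5: it omits the IVC diameter limit (inclusion 6) and states different rules for life expectancy (exclusion 15) and MELD (exclusion 22).

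*Combined protocol and SAP*

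**What the plan says.** Section 3.3 makes every inclusion criterion mandatory and requires that no exclusion applies. Section 3.4 lists six inclusion criteria. The sixth is "Mean diameter of the IVC at the right atrial junction or superior most hepatic vein", limited to 30.5 mm or less. Section 3.5 lists 22 exclusions. Number 15 is "Estimated life expectancy < 1 year from conditions other than TR". Number 22 is a MELD score of 21 or more, calculated by a cited method, "for patients not on blood thinners".

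Appendix D is a checklist whose first block is headed "Inclusion Criteria (From IRB-approved protocol" (closing bracket omitted here). It has five inclusion rows and 22 exclusion rows and ends with a statement of eligibility to be signed and dated. Row 15 gives a life expectancy under one year with no restriction on cause. Row 22 reads "MELD score >21" and nothing more. A note under the table says "All subject files must include supporting documentation to confirm subject eligibility", and radiology results are among the means it names.

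Other steps also bear on eligibility:
- Section 2.2.2 has the coordinating center review baseline echocardiograms and CT scans "to confirm severe TR and anatomic suitability for implant".
- Section 2.2.3 says "During the executive committee conference call, the local site will verify that the patient meets the" inclusion criteria and is free of the exclusions. Enrolment then needs agreement from two thirds of the committee.
- Section 5.2.1 has the IVC measured at the right atrial junction before the procedure to size the stent, by contrast CT or rotational cine fluoroscopy.

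**The concern.** The checklist presents itself as a copy of the approved criteria and carries the signature on eligibility, yet it departs from those criteria in three places.

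The missing row is the only numeric anatomic limit at the implant site. Section 5.2.1 uses the IVC diameter to size the stent that holds the valve in place, and section 4.0 lists valve embolization or migration and stent migration among the serious risks. This is the wrong criterion to leave without a prompt.

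The two altered rows mainly act in the other direction. A site that follows the form could turn away patients whom 3.5 was worded to keep, and would log screen-failure reasons that are not protocol criteria. A patient ruled out locally may never reach the executive committee, so the later checks would not correct that error.

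**Working it through.** No sample size, power or error rate is involved. The check is a row-by-row comparison of 3.4/3.5 with Appendix D.

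**Count.**
- Protocol criteria: 6 + 22 = 28.
- Checklist rows: 5 + 22 = 27, so 28 − 27 = 1 criterion is absent (inclusion 6).
- Rows present but different in substance: 2 (exclusions 15 and 22).
- Rows that agree in substance: 27 − 2 = 25.
- Criteria not reproduced: 1 + 2 = 3 of 28.

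**Is the missing row an extraction loss?** The form runs from inclusion row 5 directly to the exclusion header, the numbering is unbroken, and IVC diameter appears nowhere else on it. Both texts are current parts of the same document. A form not updated to the current criteria is the likelier explanation.

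**What each text does with each kind of patient** (on the criterion concerned only; other criteria may still exclude the patient):

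| Patient | Sections 3.4/3.5 | Appendix D | Result |
|---|---|---|---|
| Mean IVC diameter above 30.5 mm at both levels | Not eligible | Not asked | Form is silent |
| Life expectancy under 1 year because of TR itself | Not excluded | Excluded | Form too strict |
| MELD above 21, on blood thinners | Not excluded | Excluded | Form too strict |
| MELD exactly 21, not on blood thinners | Excluded | Passes, if the sign is > | Form too lenient, conditional |

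**How firm each line is.**
- The IVC line is an omission and not a contradiction: the form gives no answer on diameter.
- The two too-strict lines are firm, because they come from missing words and not from a symbol.
- The last line rests on one extracted character. The sign for 'at least' was read correctly elsewhere in Appendix D (row 4, pulmonary artery pressure), which supports reading row 22 as printed, but a reading error cannot be ruled out. If the sign were really ≥, this line would disappear, and the form would instead also exclude a MELD of exactly 21 on blood thinners. The missing restriction is therefore a mismatch under either reading.

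**Ambiguity in inclusion 6.** A diameter above 30.5 mm at both levels fails on any reading. A diameter above the limit at only one level passes if the wording means either level and fails if it means both. Taken literally, the wording points to either level, but 3.4 does not settle it.

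**The case against.** The strongest reply is that Appendix D does not decide enrolment. In the available text the body of the protocol does not send sites to it. Enrolment follows heart-team review, site verification of all criteria on the committee call, and the committee vote. The CT is required before those meetings and is reviewed centrally, and the IVC is measured for stent sizing whatever the form says. On this view the matter is an editorial correction.

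Much of that stands. The duty to meet and document inclusion 6 remains; what is missing is the prompt on the form. Two parts do not stand. Neither the central review nor the sizing step names the 30.5 mm limit, and neither helps a patient screened out locally on row 15 or 22. The form also goes beyond missing detail, because it states decision rules that differ from the protocol's.

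A reader might infer more than the documents support:
- *That patients with an oversized IVC will be implanted.* The other checks make this unlikely.
- *That the mismatch biases the results.* Section 2.3 analyses all enrolled patients regardless of eligibility and does not let the optional eligible-only analysis support conclusions.
- *That many patients are wrongly screened out.* The 33.1% one-year mortality in section 1.0 is a group death rate, not the share with an estimated life expectancy under one year. Section 5.2.1 mentions patients on warfarin but gives no frequency, and nothing on how many have a MELD above 21.
- *That the diameter is recorded nowhere.* The case report forms are not in the documents, so this cannot be judged.

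**Conclusion.** The point holds as a mismatch between a signed form and the protocol: 3 of 28 criteria are not reproduced, 1 by omission and 2 by altered wording. Used as written, the form wrongly screens out two kinds of patient, fails to prompt for the IVC limit and, if the sign in row 22 is as printed, passes a MELD of exactly 21 in a patient not on blood thinners.

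The row count describes the form. It does not measure harm or misclassification. The documents give no basis for estimating how many patients fall in these groups, and there may be none. Neither primary endpoint nor any planned conclusion changes. The correction is worth making because the mismatch is certain, it concerns patient selection for an implant, and it costs almost nothing to remove. This rests on two assumptions: that sections 3.4/3.5 are the governing text, and that sites complete Appendix D as it stands.

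**What to change.** In Appendix D, copying word for word from 3.4/3.5:

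1. Add inclusion row 6 (mean IVC diameter, limit 30.5 mm) with Yes/No boxes.
2. Replace exclusion row 15 with "Estimated life expectancy < 1 year from conditions other than TR".
3. Replace exclusion row 22 with the full text of exclusion 22: the threshold of 21 or more, the reference for the calculation, and the restriction "for patients not on blood thinners".

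A field for the measured diameter is optional. It should not be restricted to CT, because 3.4 names no modality and 5.2.1 also allows rotational cine fluoroscopy.

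Separately, the sponsor should clarify in 3.4 whether the 30.5 mm limit applies at either level or at both. The form should not choose a reading before then.

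The cost is three rows on one form, with the approval needed for a protocol change (section 6.1). The form edits need no new imaging and change no eligibility rule, sample size or analysis.

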5.1 Pre-Procedure Assessments

The following will be collected in all patients at baseline (within 90 days of procedure, except for Informed Consent which will be obtained prior to beginning screening). Items in bold font are required to determine eligibility and must be performed prior to the Heart Team and Executive Committee meetings.

- **Informed Consent**
- **Medical history.** This will include past medical and surgical history, social history, family history.
- **Physical Exam.** This will include vital signs and weight, head, ears, eyes, nose and throat (HEENT), neck, lungs, cardiovascular, abdomen, genitourinary, gastrointestinal, musculoskeletal, neurological
- **NYHA functional Class** as per The Criteria Committee of the New York Heart Association. *Nomenclature and Criteria for Diagnosis of Diseases of the Heart and Great Vessels*. 9th ed. Boston, Mass: Little, Brown & Co; 1994:253-256
- **Diuretic types and doses**
- Surgical note documenting high risk/inoperable status.

Laboratory Measurements

- CBC with differential (During 6 months of screening and within 21 days of procedure)
- Cardiac Enzymes (Troponin I and/or CK and CKMB) (≤ 72 hours before the procedure)
- **Comprehensive metabolic panel** (within 90 days of procedure)
- Lactate Dehydrogenase (LDH)
- ACT (within 21 days of procedure)
- aPTT (within 21 days of procedure)
- **PT/INR** (within 90 days of procedure)
- Brain Natriuretic Peptide (BNP) (within 21 days of procedure)

Non-Invasive Tests

- ECG (within 21 days of procedure)
- Chest X-ray (portable or PA and lateral) (within 21 days of procedure)
- **Echocardiogram** (Transthoracic) (within 90 days of procedure)
- **Chest and Abdominal CT** (within 90 days of procedure)
- Cardiopulmonary Exercise Stress test ³² (within 90 days of procedure)
- Venous Lower Extremity Duplex Study (within 21 days of procedure)
- **Pulmonary Function Testing** (PFT) (within 90 days of procedure)

Functional Assessments

- 6-minute walk test ³³ (within 90 days of procedure)
- Villalta Scale ^{25,26} (within 21 days of procedure)
- EORTC QLQ-C30 ²⁷ (within 21 days of procedure)
- ESAS-AM ²⁸ (within 21 days of procedure)
- Kansas City Cardiomyopathy Questionnaire (KCCQ) ²² (within 21 days of procedure)

Invasive Tests

- **Left Heart Catheterization with or without LV gram and IVUS.** (Within one year of baseline)
- **Right Heart Catheterization** (within 90 days of procedure)

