5.6 Annual Study Visit, Final Study Visit, premature discontinuation or unscheduled study visit

The following variables will be collected for the above parameters.

- Physical Exam. This will include vital signs and weight, head, ears, eyes, nose and throat (HEENT), neck, lungs, cardiovascular, abdomen, genitourinary, gastrointestinal, musculoskeletal, neurological
- NYHA functional Class as per The Criteria Committee of the New York Heart Association. *Nomenclature and Criteria for Diagnosis of Diseases of the Heart and Great Vessels*. 9th ed. Boston, Mass: Little, Brown & Co; 1994:253-256
- Diuretic types and doses
- Event assessment as per VARC-2 ¹⁹.

Table 1: Summary Schedule of Procedure and Follow-Up

	Baseline	During the procedure	24 hrs. after the procedure	7 days after procedure or at discharge	At 30 days (+/- 7 days)	At 6 months (+/- 14 days)	At 1 yr (+/- 21 days)	Annually up to 5 years (+/- 21 day)	Premature discontinuation or unscheduled visit
Informed Consent	Xb†								
Medical History	Xb†								
Physical Exam (incl. Vital signs)	Xb†		X	X	X	X	X	X	X
NYHA Class	Xb†		X	X	X	X	X	X	X
Diuretic types and doses	Xb†		X	X	X	X	X	X	X
Event Assessment	Xb		X	X	X	X	X	X	X
Surgical note documenting high risk/inoperable status	Xb†								

Laboratory Measurements								
CBC with Differential	Xd		x	X		X	X	
Cardiac Enzymes (Troponin I and/or CK and CK-MB)	Xe		X (every 8 hours x 3)					
Comprehensive Metabolic Panel	Xb†		X	X	X	X	X	
LDH (to assess hemolysis)	Xc		X	X	X	X	X	
ACT^		X*	X*					
aPTT	Xc	X*						
PT/ INR	Xb†		X					
Brain Natriuretic Peptide (BNP)	Xc		x	X	X	X	X	
Haptoglobin	Xc			X	X	X	X	
Non-Invasive Tests								
ECG	Xc		X		X	X	X	
Chest X-ray	Xc				X	X	X	
Echocardiogram - TTE or TEE	Xb†	X	X		X	X	X	
Chest and/or Abdominal CT	Xa†					X		
Cardiopulmonary Exercise Stress test	Xb					X		
Venous Lower Extremity Duplex Study	Xc							
Pulmonary Function Test (PFT)	Xb†							
Functional Assessments								
6-Minute Walk Test	Xb				X	X	X	
Quality of Life (Kansas City Cardiomyopathy Questionnaire (KCCQ))	Xc				X	X	X	
Villalta Scale	Xc				X	X	X	
EORTC QLQ-C30	Xc				X	X	X	
ESAS-AM	Xc				X	X	X	
Invasive Tests								
Left Heart Catheterization w/wo LV gram and IVUS ^a	Xa†	X*						
Right Heart Catheterization	Xb†	X				X		

- a. The following assessment will be collected within one year of procedure day.
- b. The following assessments will be completed within 90 days before the procedure day

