
1. Heart Team assessment of operability (the heart team considers the patient to be a good surgical candidate)
			

2. Evidence of an acute myocardial infarction \leq 1 month (30 days) before the intended treatment [defined as: Q wave MI, or non-Q wave MI with total CK elevation of CK-MB \geq twice normal in the presence of MB elevation and/or troponin level elevation (WHO definition)]
			

3. Untreated, severe, left sided valvular heart disease including mitral regurgitation or stenosis, and aortic regurgitation or stenosis
			

4. Mean pulmonary artery pressures ≥ 40 mmHG and PVR > 4 Woods units as assessed by right heart catheterization			
5. Any therapeutic invasive cardiac procedure resulting in a permanent implant that is performed within 30 days of the index procedure. Examples of permanent implant would include any new heart valve. Implantation of a permanent pacemaker is excluded.			
6. Patients with planned concomitant surgical or transcatheter ablation for Atrial Fibrillation			
7. Leukopenia (WBC < 3000 cell/mL), acute anemia (Hgb < 9 g/dL), Thrombocytopenia (Plt $< 50,000$ cell/mL)			
8. Hemodynamic or respiratory instability requiring inotropic support, mechanical ventilation or mechanical heart assistance within 30 days of screening evaluation			
9. Need for emergency surgery for any reason			
10. Left ventricular ejection fraction $< 40\%$			
11. Echocardiographic evidence of intra-cardiac mass, thrombus or vegetation			
12. Active upper GI bleeding within 3 months (90 days) prior to procedure			
13. A known contraindication or hypersensitivity to all anticoagulation regimens, or inability to be anticoagulated for the study procedure			

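### Exclusion 7 states its white-cell and platelet limits per mL, so read literally those two limbs cannot exclude a realistic candidate; the blood count it relies on also lacks the protocol's pre-meeting mark

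*Combined protocol and SAP*

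**What the plan says.** **The limits.** Section 3.5, exclusion 7, lists three hematological conditions. It begins "Leukopenia (WBC < 3000 cell/mL), acute anemia (Hgb < 9 g/dL" and continues "Thrombocytopenia (Plt $< 50,000$ cell/mL". The Appendix D checklist, which ends in a signed statement of eligibility, has the same criterion with the same unit: "Leukopenia (WBC < 3000 cell/mL), acute anemia (Hgb < 9 g/dL), Thrombocytopenia".

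**The test that feeds the criterion.** Section 5.1 sets a marking rule: "Items in bold font are required to determine eligibility and must be performed prior to the Heart Team and Executive Committee meetings". It then lists "CBC with differential (During 6 months of screening and within 21 days of procedure" in ordinary type. The "Comprehensive metabolic panel (within 90 days of procedure" entry is in bold, as is PT/INR.

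Table 1 uses a dagger for the same purpose. The row "CBC with Differential" has the baseline code Xd with no dagger, while the metabolic panel and PT/INR rows have Xb with a dagger. Footnote d asks for a CBC during the six-month screening period and again within 21 days before the procedure.

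**The enrollment step.** Under section 3.2 the case goes to the heart team once screening is complete, and a two-thirds vote of the executive committee enrolls the patient. Under section 2.2.3 the site must confirm on the committee call that the patient meets the "inclusion, and is free from exclusion criteria for the trial".

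**The concern.** A count limit does its work only through its number and its unit. The condition names show that exclusion 7 is meant to keep out patients with low white-cell or platelet counts. If the unit makes the limit unreachable, the signed form records a check that cannot fail on those two limbs. The platelet limb matters for safety, because patients receive heparin during the procedure (section 5.2.1) and the recommended regimen afterwards is aspirin plus warfarin.

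The second matter is one of consistency. The protocol has two ways of marking the tests that must be in hand before the heart team and executive committee meet. The only test that can inform exclusion 7 carries neither mark.

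**Working it through.** **1. Unit conversion.** The limits are not derived from other figures in the plan, so there is no stated result to reproduce. The check is 1 mL = 1,000 microliters.

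- White cells: 3,000 per mL / 1,000 = 3 per microliter.
- Platelets: 50,000 per mL / 1,000 = 50 per microliter.
- Hemoglobin: 9 g/dL needs no conversion and works as written.

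**2. Can the written limits exclude anyone?** The documents give no patient counts, so the values below are assumptions chosen to run from very low upward.

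| Assumed count per microliter | Same count per mL | Multiple of the written limit | Excluded as written? | Excluded if the limit were per microliter? |
|---|---|---|---|---|
| WBC 100 | 100,000 | 100,000 / 3,000 = 33 | No | Yes |
| WBC 2,000 | 2,000,000 | 2,000,000 / 3,000 = 667 | No | Yes |
| WBC 4,000 | 4,000,000 | 4,000,000 / 3,000 = 1,333 | No | No |
| Platelets 1,000 | 1,000,000 | 1,000,000 / 50,000 = 20 | No | Yes |
| Platelets 20,000 | 20,000,000 | 20,000,000 / 50,000 = 400 | No | Yes |
| Platelets 150,000 | 150,000,000 | 150,000,000 / 50,000 = 3,000 | No | No |

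No assumed value meets either written limit. If the same numbers were meant per microliter, they would equal 3,000,000 white cells and 50,000,000 platelets per mL, which is 1,000 times what is written.

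**3. Marking of the CBC.** Other measured criteria can be set beside the test that informs them.

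| Criterion | Test | Bold in 5.1 | Dagger in Table 1 |
|---|---|---|---|
| Exclusion 4 (pulmonary pressure, PVR) | Right heart catheterization | Yes | Yes |
| Exclusion 10 (LVEF) | Echocardiogram | Yes | Yes |
| Exclusion 21 (FEV1) | Pulmonary function test | Yes | Yes |
| Inclusion 6 (IVC diameter) | CT | Yes | Yes |
| Exclusion 7 (WBC, hemoglobin, platelets) | CBC | No | No |

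The second CBC, within 21 days, is counted back from the procedure. Section 2.2.3 sets the implantation date only on approval, so that CBC can fall after the vote. The screening CBC is therefore the one that should carry the pre-meeting mark.

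**The case against.** **The unit may be a lost micro sign.** No micro sign appears anywhere in the extracted text. The kidney-injury table in Appendix B pairs 0.3 mg/dL of creatinine with 26.4 mmol/L, and 4.0 mg/dL with 354 mmol/L. These pairs agree only in micromoles per liter, so they are off by the same factor of 1,000. That pattern fits a symbol lost in typesetting or in reading the PDF. It is not proof, because the table is reproduced from elsewhere and may carry the slip from its source. The possibility stands, and it is the reason to look at the source file before amending anything.

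**Few readers would apply the limit literally.** Each number is attached to a named condition, the checklist requires supporting documents such as laboratory results, and exclusion 13 separately bars patients who cannot be anticoagulated for the procedure. A reader might infer that a severely thrombocytopenic patient would pass. That would require the site, the heart team and two-thirds of the committee all to disregard the named condition and convert the laboratory report to per mL. The documents give no reason to expect that. This objection stands as to effect, but not as to the text.

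**A screening CBC is already required.** A reader might infer from the missing marks that a patient can be enrolled before exclusion 7 has to be checked. The documents do not support that. Footnote d requires a CBC during screening, section 3.2 presents the case once screening is complete, section 3.3 requires freedom from every exclusion, and section 2.2.3 has the site confirm this on the call. What remains is a marking inconsistency.

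**An ineligible patient would shift the endpoints.** This too might be inferred, since section 2.3 keeps every enrolled patient in the analysis. But one patient in 15 carries the same weight whatever the reason for enrollment, ineligibility does not make an endpoint value wrong, and section 2.3 also allows a secondary analysis of eligible patients. This is not a measure of the defect.

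**Conclusion.** The point holds as an error in an eligibility threshold that appears in both the protocol and the signed checklist. As written, two of the three limbs of exclusion 7 cannot exclude a realistic candidate. The size is a factor of 1,000 on each of the two limits, on the assumption that per microliter was intended. That assumption rests on the condition names; the documents do not state the intended unit. The finding that no realistic candidate is caught rests on the assumed counts in the table, the lowest of which are 33 times (white cells) and 20 times (platelets) the written limits.

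The practical effect is probably small, because sites are likely to apply usual laboratory units. Sample size, confidence intervals and stopping boundaries are untouched. The correction is still worth making, because an eligibility form should not depend on readers silently changing its unit.

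The CBC marking is a secondary inconsistency. The protocol already places a blood count and a check of the exclusions before the vote, but its own marking does not list that blood count among the tests required for it.

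**What to change.** 1. The sponsor should compare the unit in section 3.5 and Appendix D with the source file. If the per-mL unit is really there, the sponsor should confirm the intended unit and correct exclusion 7 in both places. If the source already shows another unit, no change to the limits is needed.
2. Put the screening CBC in bold in section 5.1 and add the dagger to its baseline entry in Table 1. Because one code, Xd, covers both blood counts, footnote d should say that the dagger belongs to the screening count.
3. Keep the CBC within 21 days of the procedure as planned.

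The cost is a unit correction in two places, two marks and a few words in a footnote, submitted with the IRB approval that section 6.1 requires for any protocol change. No test, visit or analysis is added.
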